This registry will prospectively collect data from young adult cancer survivors using electronic surveys to describe patient-reported needs and outcomes at baseline as well as changes over time. Please note that all information collected for this registry is self-reported and not confirmed.

Registry Site(s)/Location(s) and Number of Subjects

YASU website registration page: yasurvivors.org

Total number of all sites: 1

Estimated number of subjects at all sites combined: undetermined. ongoing recruitment will occur as members register with the organization.

Subject Selection

Vulnerable Populations (if applicable)

N/A

Participant Selection

Inclusion Criteria

1. Diagnosed with cancer between the ages of 18 and 39.
2. Able to speak and read English.

This registry is designed to explore the specific concerns, needs, and outcomes of those diagnosed with cancer as YAs (ages 18-39). Potential participants will be required to comprehend English as some of the surveys we will administer have not been validated in other languages. Additionally, YASUs programming is conducted in English. Without the ability to comprehend English, individuals would not be able to participate in YASU programming and we would not be able to test for possible mediation, as listed in Aim 2.

Exclusion Criteria

1. Inability to provide consent (such as neurological illness or mental incapacity)
2. Has not registered as a member of YASU

Waiver of Written Documentation of Consent or Waiver of Consent

We are applying for a Waiver of Written documentation of Consent (consent will be obtained but signatures will not be required) as this study is minimal risk and will be conducted completely electronically.

Registry Procedures

Specific Training

After IRB approval and prior to study initiation, the PI will meet with members of the YASU organization to explain the registry and procedures for consent and data collection and their roles and duties including answering any questions or concerns that may arise. Besides an email sent to current YASU members inquiring about their interest in research registry participation, the consent for new members and ongoing surveys for those who consent to participate will be automatically triggered and sent (using Salesforce) so we do not anticipate needing significant involvement from YASU organizational staff members for ongoing study management.

Recruitment of participants

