Cancer survivors will be asked for consent at the time of registration with YASU or (in the case of those who have already registered) with an email sent to describe study and providing an opportunity to give consent and participate in the registry. Baseline and annual follow-up data will be collected according to the table below. In addition, participation in organizational sponsored programs (e.g., socials, support groups, financial assistance) will be recorded and included in the research registry.

	Instrument	# Items (Approx. time)	Assessment Time Points	
			Baseline	6 mos., then Yearly
Demographics Race Gender DOB Address			✓ ✓ ✓ ✓	
Disease and treatment information Age at Diagnosis Type of cancer Stage Treatment			✓ ✓ ✓ ✓	
Change in disease or treatment	Compared to a year ago, is your health: better, about the same, or worse [If better or worse, then allow free text to explain why]			✓
Depression	PHQ-9	9 (2 min)	✓	✓
Anxiety	GAD-7	7 (1-2 min)	✓	✓
Distress	Distress Thermometer (included in AYA-POST)	1 (30 sec)	✓	✓
Needs Assessment	AYA Psycho-Oncology Screening Tool (AYA-POST)	50 (5 min)	✓	
Financial Toxicity	COST – FACIT (Ver 2)	12 (3 min)	✓	✓
Social support survey instrument	MOS Social Support Survey Instrument	19 (5 min)	✓	✓

Baseline= day of enrollment in the program

Surveys completed ±2 weeks from targeted timeframe

Registry Duration

Registry enrollment will be ongoing. Participants will remain active in the registry until they voluntarily withdraw or expire. Any data that has been provided up until that point will continue to be included in the registry.

Data Management and Quality Plan

Data De-identification

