Patient Health Questionnaire 9 (PHQ-9) (Pfizer, 2010): The PHQ-9 is a 9-item self-reported instrument designed to assess depressive symptoms. For each of the questions, individuals choose one of the following responses regarding how they have been feeling in the past two weeks: Not at all (0), Several days (1), More than half the days (2), or nearly every day (3). The responses can be summed together to yield a total score from 0-27, with higher scores indicating more depressive symptoms. The PHQ-9 will be completed electronically via survey at baseline and annually.

Generalized Anxiety Disorder (GAD-7) (Pfizer, 2010): The GAD-7 is a self-administered 7-item instrument to measure anxiety symptom severity. Like the PHQ-9, individuals think about how they have been feeling in the past two weeks and choose from the following answers: Not at all

(0), Several days (1), More than half the days (2), or nearly every day (3). Total scores range from 0-21, with higher scores indicating greater anxiety symptom severity.

Adolescent and Young Adult Psycho-Oncology Screening Tool (AYA-POST) (Patterson et al., 2022): The AYA-POST provides a psychosocial screening and assessment for people diagnosed with cancer. The tool comprises a distress thermometer and age-specific needs assessment. The distress thermometer quantifies the amount of self-reported distress an individual has experienced over the past week ranging from 0 (no distress) to 10 (high distress). The needs assessment identifies areas of distress or concern in the following categories: practical, family, emotional, social, physical, information, and other (which allows for free response).

Comprehensive Score for financial Toxicity-Functional Assessment of Chronic Illness Therapy (COST-FACIT) (Version 2) (FACITgroup, 2017): The COST-FACIT is a 12-item patient reported measure of financial distress for cancer patients. The measure provides a summary score for financial toxicity. Scores range from 0-44 with higher scores indicating better financial wellbeing.

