MOS Social Support Survey Instrument (Sherbourne & Stewart, 1992): The Social Support Survey is a self-administered, multidimensional social support survey that was specifically developed for patients with chronic health conditions. This 19-item measure consists of four separate social support subscales (emotional/informational support; tangible support; affectionate support; positive social interaction) and an overall functional social support index. Higher scores in the subscale and the overall support index indicate more support.

Statistical Analysis Plan

Aim 1 is to describe patient-reported symptoms (depression, anxiety, distress), perceived social support, financial toxicity and needs in survivors of young adult cancer at baseline and over time. Baseline data will be summarized using descriptive statistics appropriate to the variable's level of measurement. Repeated measures analysis of variance will be used to measure changes over time.

Aim 2 is to determine effectiveness of YASU programming by examining its possible mediation on the measures of Aim 1. This will be assessed via mediation analysis suited to longitudinal data, such as a natural effect models (Mittinty & Vansteelandt, 2020).

Once data are gathered we will determine whether to exclude missing data pair-wise or whether we plan to impute missing values, depending on the variable and the amount of missing data within and between cases.

Potential Risks and Benefits

Potential Benefits

There are no direct benefits to subjects for participating in this research registry. However, information regarding needs and wellbeing of young adult cancer survivors may result from this registry.

Potential Risks

This research represents a registry documenting the needs and outcomes of young adult cancer survivors. The most likely risk posed to participants would be a breach of confidentiality if someone other than the research team obtained access to the data.

We do not anticipate that completing registry surveys will increase the risk of depression or suicide, however these things may be reported on the depressive symptom measure. Resources for those that report suicidality will be provided including a suicide hotline and links to mental health resources.

Mitigation of Risks

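### Aim 1 change over time rests on repeated-measures ANOVA with the missing-data rule left open, although the design makes survey numbers unequal; a prespecified mixed model is a cheap improvement of modest expected size

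*Combined protocol and SAP*

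**What the plan says.** The Statistical Analysis Plan names one method for Aim 1 change: "Repeated measures analysis of variance will be used to measure changes over time". It gives no covariance structure, list of waves or analysis population. On missing data it says "Once data are gathered we will determine whether to exclude missing data pair-wise or whether we plan to impute missing values". That choice is to turn on which variable is affected and how much is missing. The plan does not define pair-wise for a missing wave, and it names no missing-data assumption or sensitivity analysis.

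The design makes the data unbalanced. Under Registry Site(s)/Location(s) and Number of Subjects, "ongoing recruitment will occur as members register with the organization". Under Registry Duration, "Registry enrollment will be ongoing" and "Participants will remain active in the registry until they voluntarily withdraw or expire". Investigator Withdrawal of Subjects keeps a person who misses a survey window in the registry and counts that survey as missing. Data Collection and Follow-up for Withdrawn Subjects promises that data given before withdrawal will be analysed.

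The set of waves is not settled. The table under Data Collection Schedule has "6 mos., then Yearly", and Subject Stipends or Payments gives 6, 12 and 24 months as examples. Registry Data Points, however, says "The PHQ-9 will be completed electronically via survey at baseline and annually", and Investigator Withdrawal of Subjects also describes yearly surveys.

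**The concern.** In its classical form, and without imputation, repeated-measures ANOVA uses only people with every included wave. At any data cut, recent entrants will not have reached the later waves, and missed windows add gaps. People who withdraw before the last included wave would also drop out, although the plan says their data will be analysed.

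The missing-data rule does not settle the matter, because it is chosen after the data are seen and may differ by variable. It also does not distinguish a survey that was due and not returned from one that is not yet due.

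Aim 1 is descriptive and no sample size or power is stated. What is at stake is the precision, and to a lesser degree the bias, of the reported change.

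**Working it through.** There is no figure in the plan to reproduce. Only the schedule comes from the documents; every other input is an assumption.

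**Inputs.** Waves at 0, 6, 12 and 24 months (schedule table and stipend text), or 0, 12 and 24 months if surveys are annual. Assumed correlations are 0.65, 0.58 and 0.50 for waves one, two and three steps apart (without the 6-month wave: 0.58 for 0-12, 0.65 for 12-24 and 0.50 for 0-24 months). The target is 24-month minus baseline change. Variances are in units of SD²/N.

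**1. Non-response alone.** Completion is p at each of w follow-ups, independently.
- Listwise variance: 2(1 − 0.50)/p^w = 1/p^w.
- Paired variance (everyone with baseline and 24 months): 1/p.
- Likelihood variance: c′I⁻¹c, where I sums, over response patterns, the pattern's probability times the inverse correlation matrix of the observed waves.
- Extra width: the square root of the variance ratio, minus 1.

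| w = 3 | p = 0.95 | p = 0.80 | p = 0.60 |
|---|---|---|---|
| People with all waves, p³ | 0.857 | 0.512 | 0.216 |
| Listwise variance | 1.166 | 1.953 | 4.630 |
| Paired variance | 1.053 | 1.250 | 1.667 |
| Likelihood variance | 1.028 | 1.140 | 1.396 |
| Listwise interval wider by | 6.5% | 31% | 82% |
| Paired interval wider by | 1.2% | 4.7% | 9.3% |

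With two follow-ups the listwise interval is 4%, 17% or 40% wider, and the paired interval 1.1%, 4.3% or 8.4% wider.

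**2. Rolling entry alone, everyone responding, data cut at 36 months.** If entry is uniform, the shares due at 6, 12 and 24 months are 30/36, 24/36 and 12/36. The all-waves analysis leaves 1 − 3×12/(30 + 24 + 12) = 45% of returned follow-up surveys unused. Variances are 3.00 against 2.136, so the interval is 18.5% wider. If half enter at the start, the shares due are 0.917, 0.833 and 0.667, and 1 − 3×0.667/2.417 = 17% are unused. Variances are 1.50 against 1.297, so the interval is 7.6% wider. Here everyone who has reached 24 months has all waves, so listwise and paired exclusion coincide.

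**3. Bias in 24-month change when the true change is zero.** Simulation with PHQ-9 SD 5.5, 20% dropout per wave and log-odds of dropout 0.3 to 0.8 per SD, three follow-ups.
- Dropout depends on earlier scores (MAR): completers +0.15 to +0.36 points (a repeat gave +0.16 to +0.37), about 0.03 to 0.07 SD. The likelihood model with unstructured covariance and multiple imputation were within 0.01 of zero.
- Dropout independent of scores (MCAR): all within 0.01 of zero, so only precision is lost.
- Dropout depends on the unseen score (MNAR): completers −0.17 to −0.41; likelihood and imputation −0.34 to −0.88.

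**4. Choice of fallback covariance.** First-order autoregression by nominal wave treats the 0-6, 6-12 and 12-24 month gaps as equal. It implies correlations of 0.65, 0.65² = 0.42 and 0.65³ = 0.27, against the assumed 0.65, 0.58 and 0.50. Fitted to the MAR simulation it gave bias of −0.12 to −0.30 points, close in size to the completer bias.

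**The case against.** The strongest reply is that the plan does not commit to complete cases. It names pair-wise exclusion or imputation. Imputation, well specified, largely solves the problem under MAR. Pair-wise exclusion in its ordinary paired sense costs about 1% to 9% in interval width under non-response. This stands. A reader might infer that the plan will discard most of its surveys or report intervals 82% wider. The documents do not support that: it needs listwise exclusion, which they do not name, and 60% completion, which they do not state.

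Entry is also unlikely to be uniform. Recruitment of participants has existing members emailed after approval, and the background puts membership near 500, so entry may be front-loaded. Uptake is unknown. This too stands, and it is why the half-at-start case is shown.

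A reader might also infer serious bias. In the same MAR simulation, separate unpaired wave means were off by −0.57 to −1.33 points, but that is not a within-person analysis and the plan does not propose it. Nor is the mixed model a cure for every mechanism: under the simulated MNAR dropout it was about twice as far off as completers.

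What remains is that the named ANOVA does not fit data that are unbalanced by design. The rule that might rescue it is undefined for missing waves and deferred until the data are gathered.

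**Conclusion.** The point holds as a cheap improvement in method. It does not show that Aim 1 would fail. Ongoing entry and open-ended follow-up make unequal numbers of surveys certain; how much that costs is not known.

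Under the stated assumptions, the loss of precision runs from about 1% to 9% (paired) to 6.5% to 82% (listwise) for non-response, and from about 8% to 18.5% for rolling entry alone at a 36-month cut. Completer bias under MAR is small. No loss of power can be claimed, because the plan states neither power nor a sample size.

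Confidence is high that the method and design are mismatched and that the rule is deferred. It is lower for the magnitudes. The change is worth considering, at most at the low end of what the sponsor should do.

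**What to change.** Before analysis, and for Aim 1 change only:

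- Replace the ANOVA sentence with a REML linear mixed model on all observed surveys for PHQ-9, GAD-7, distress thermometer, COST-FACIT and MOS, with categorical wave and unstructured within-person covariance. State that it replaces pair-wise exclusion for missing waves and assumes MAR. Multiple imputation is an acceptable equivalent. Under the current window rule, observed means returned in the window.
- If the unstructured model does not converge, drop sparsely observed late waves, or use a structure that respects the unequal spacing and slow decay of correlation, such as heterogeneous Toeplitz or factor-analytic. Do not fall back on first-order autoregression by nominal wave.
- Keep covariates optional, or give a rule so that a missing covariate does not remove a person.
- Treat surveys not yet due as administratively unobserved. Apply a delta-adjusted MNAR sensitivity analysis only to surveys that were due and not returned, over a stated range of shifts. As an illustration, the simulated MNAR cases needed 0.13 to 0.39 SD to restore zero change, so −0.4 to +0.4 SD would cover them; that range depends on the assumed dropout.
- Reconcile the 6-month wave with the annual wording and list the waves to be analysed.

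The cost is SAP wording and slightly more analysis work, with no new data collection. The primary result would still rely on MAR.

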In 2007, the Adolescent & Young Adult Health Outcomes & Patient Experience Study (AYA HOPE) study was conducted in patients diagnosed between the ages of 15 and 39 with one of the following cancers: germ cell, Hodgkin lymphoma, non-Hodgkin lymphoma, acute lymphoblastic leukemia (ALL), or sarcoma (Ewing, osteosarcoma, or rhabdomyosarcoma). Altogether, AYA HOPE includes approximately 530 AYA cancer patients with follow-up approximately 24 months post-diagnosis. Participants were recruited from one of the following SEER cancer registries: Los Angeles, Seattle-Puget Sound, Iowa, Louisiana, Detroit, Northern California, and Greater California. This study concluded in July, 2010. AYA HOPE is an important study which provides a preliminary framework to describe the unique challenges of AYA diagnosed with cancer, (namely, financial burden, education and work, relationships and family planning, as well as physical and mental health), however many YA cancers were not represented in this dataset and only individuals from certain parts of the country were included. Furthermore, the study only includes one follow-up and the study is no longer gathering data.

There is a lack of age-relevant support and resources as well as a gap in the knowledge of the needs and outcomes of YAs with cancer. YASU has a unique opportunity to add to the literature by surveying participants in an ongoing manner from its members in Western Pennsylvania, across the country, and around the world. This dataset will help to explore the unmet needs of YAs with cancer, determine effectiveness of programming, as well as plan for future programming to serve this population. In the future, we hope to be able to also make this dataset available to other academicians and researchers interested in improving the health and wellbeing of YA survivors with cancer.

Registry Specific Aims

Through this research registry we plan to:

1. Objectively measure patient-reported symptoms (depression, anxiety, distress), perceived social support, financial toxicity and needs in survivors of young adult cancer at baseline and over time.
2. Determine effectiveness of YASU programming by examining its possible mediation on the measures of Aim 1.
3. Identify patients who may be eligible for participation in future research studies.

Registry Design

Research Design

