YASU members who have already registered with the organization will receive an email providing an overview of the registry at a time point after IRB approval for the registry has been secured. No previous data they provided will be used in the research registry. Only information that they provide in the future will be used. Any new members registering with YASU will be provided with this information at the time of registering with the organization. If the member would like to participate in the research registry, they may access a webpage (data security measures are discussed later in the protocol) which will provide an overview of the purpose of the study and expectations. Potential participants will be informed that their participation in the registry is voluntary and will not in any way change their relationship with the YASU organization. Potential participants will be given as much time as they need to review the study description and will be provided with the PI's and/or a YASU staff member's email to answer any questions they may have before providing consent via the webpage. Additionally, for any current members, we will offer a virtual session to describe the study and

provide a forum for questions, should they so choose. Potential participants will not be required to attend the virtual session; they may also choose to email the PI or YASU staff members with questions, if they prefer.

Participants will be offered two levels of consent. They will be asked to enter the registry for research purposes. They will also choose to opt-in or opt-out of consenting to future contact [for further follow-up or for invitation to participate in additional research studies]. “Opting-in” to future contact will allow us to use the contact information they provided to YASU to facilitate future contact (e.g. name, email address, phone numbers, mailing address) for researchers who have received approval from YASU. Participants will provide consent electronically by certifying they have read the information sheet and either agree or do NOT agree to participate in the registry. They will also either choose to agree to future contact for research or NOT agree to future contact for research.

Data Collection Schedule

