Security measures in place to prevent breach of confidentiality from happening (e.g. using Salesforce, an application that upholds HIPAA privacy and security measures; employing features such as limiting access to identifiable data to only users that are associated with the registry).

Participants' responses to the depression inventory scale (PHQ-9) will be monitored. Resources for those that report suicidality will be provided including a suicide hotline and links to mental health resources.

Provisions to Protect the Privacy Interest of Registry Participants

All precautions will be taken to make sure that only authorized individuals will be accessing subject research records. The collection of sensitive information about subjects is limited to the amount necessary to achieve the aims of the research registry, so that no unneeded sensitive information is being collected.

Early Withdrawal of Subjects

Investigator Withdrawal of Subjects

Research registry participants will continue to be surveyed annually. If a participant does not complete surveys within the 4-week "grace period" (± 2 weeks from targeted timeframe) the survivor will not be withdrawn from the registry, but these surveys will be considered as missing data in the data set.

Subject Request for Withdrawal from Registry

Patients wishing to withdraw their data from the research registry will be directed to contact the principal investigator. From the point of withdrawal, no further data will be collected from the patient or their medical records. However, any data collected up to the point of withdrawal will be maintained for integrity of the research registry. Patients will be made aware of their rights in the consent.

Data Collection and Follow-up for Withdrawn Subjects

Patients who withdraw from the registry will have their data maintained in the research database up to the point of withdrawal. This data will be included in subsequent analysis.

Adverse Event Reporting

Adverse Events

N/A; This is an observational registry that does not include a planned intervention or exposure.

Ethical Considerations

N/A

Sharing of Results with Subjects

Individual participant results will not be shared with subjects or others. General results from aggregate data may be shared with participants.

Funding Source

Staunton Farm Foundation (07/01/23-06/30/24)

Elsie H. Hillman Foundation (07/01/23-06/30/25)

Subject Stipends or Payments

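### Aim 2 seeks the effectiveness of YASU programming, but its mediation analysis names no exposure, contrast or confounders, so the plan does not secure an estimate of the programme effect

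*Combined protocol and SAP*

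**What the plan says.** The second aim under Registry Specific Aims reads: "Determine effectiveness of YASU programming by examining its possible mediation on the measures of Aim 1". The Statistical Analysis Plan repeats it and gives one method: "This will be assessed via mediation analysis suited to longitudinal data, such as a natural effect models". The rationale for requiring English returns to the same test, saying that without English "we would not be able to test for possible mediation, as listed in Aim 2".

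On who is studied, the inclusion criterion is "Diagnosed with cancer between the ages of 18 and 39" and an exclusion criterion is "Has not registered as a member of YASU". On what is collected, the Data Collection Schedule states that "participation in organizational sponsored programs (e.g., socials, support groups, financial assistance) will be recorded and included in the research registry". Repeated symptom, financial and social support scores are collected, together with demographics, age at diagnosis, cancer type, stage and treatment (Data Collection Schedule; Registry Data Points). For members who joined before the registry opened, Recruitment of participants says "No previous data they provided will be used in the research registry".

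The documents do not say which variable is the exposure in the mediation analysis, which levels of participation are compared and over what period, or which covariates are adjusted for. The only other longitudinal analysis, the repeated measures ANOVA for Aim 1, states no programme term.

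**The concern.** A mediation analysis needs an exposure, a mediator and an outcome. The outcomes are given: the Aim 1 measures. The phrase about programming and its possible mediation puts programming in the mediator's place. The exposure is then missing, and natural direct and indirect effects have no definition until one is supplied. The eligibility criteria rule out the two obvious candidates, because membership and a cancer diagnosis do not vary within the registry.

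If an analyst supplies some other exposure, such as stage, the indirect effect is the part of the effect of stage that runs through programming. That answers a different question from whether programming helps.

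Participation is also self-selected. Members in greater distress or hardship may be the likelier users of support groups and financial assistance. If so, any programme coefficient that does not account for preceding need is biased against the programme. What is at stake is the conclusion of Aim 2. Aims 1 and 3 do not depend on it.

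**Working it through.** The plan states no sample size, power or effect for Aim 2, so there is no figure to reproduce. The textual gap is established by the passages quoted above. The numbers below only show how much it could matter. **All inputs are assumed**: outcome SD 5.5, true programme effect -2.0 PHQ-9 points, 1,000,000 simulated subjects per scenario.

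**1. Programming as mediator.** Let X be a binary exposure supplied by the analyst, M participation and Y the next score, with Y = 9 + 1.0X - 2.0M + error. In this linear model, indirect effect = (difference in participation between levels of X) x (-2.0).

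| Participation difference | Product | Simulated |
|---|---|---|
| -0.8 | +1.6 | +1.59 |
| -0.5 | +1.0 | +1.00 |
| -0.3 | +0.6 | +0.60 |
| 0 | 0.0 | 0.00 |
| +0.3 | -0.6 | -0.60 |
| +0.5 | -1.0 | -1.00 |
| +0.8 | -1.6 | -1.62 |

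The programme is equally effective in every row. The indirect effect equals -2.0 only if X fully determines participation (difference +1). A positive value does not mean harm; it means that X lowers participation.

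**2. Using the programme-to-outcome coefficient instead.** In the models above nothing confounds it, and it is -1.99 to -2.03. Now let the preceding score z (in SD units) drive participation: logit P(M) = -0.4 + 0.5X + kz, and Y = 9 + 1.0X - 2.0M + 5.5(0.6z + 0.8e), with e standard normal.

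| k (log-odds per SD) | Adjusted for X only | Adjusted for X and z |
|---|---|---|
| 0.25 | -1.20 | -2.00 |
| 0.5 | -0.44 | -2.01 |
| 1.0 | +0.72 | -2.01 |

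**3. Why all preceding scores are needed.** Let preceding financial hardship c (correlation 0.4 with preceding PHQ-9) drive participation, with logit P(M) = -0.8 + kc and next PHQ-9 = 9 - 2.0M + 5.5(0.55z + 0.2c + 0.75e). Adjusting for preceding PHQ-9 alone gives -1.55 (k = 0.5) and -1.21 (k = 1.0). Adjusting for both gives -1.99 and -2.00.

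**4. Why concurrent programmes belong in one model.** Suppose programme A does nothing, programme B has effect -2.0, and a shared factor drives uptake of both (log-odds 0.5, 1.0, 2.0 per SD). Comparing users of A with members who used nothing credits A with about -0.9, -1.0 and -1.3. This is -2.0 times the share of A users who also use B, so it corresponds to shares of about 45%, 50% and 65%. Entering A and B jointly returns 0 for A.

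**5. Why the participation measure must be fixed in advance.** The follow-ups listed under Subject Stipends or Payments (6, 12 and 24 months) give intervals of 6, 6 and 12 months. With P(any participation) = 1 - exp(-0.1 x months), this is 0.45 over 6 months and 0.70 over 12. If scores drift by -1 or -2 points per 6 months and the programme has no effect, an any-versus-none contrast that ignores interval length gives -0.23 or -0.45. Including length gives -0.01 in both cases. With participation per month as the exposure, the coefficient is about 0 (-0.02 and +0.04) without that adjustment.

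**6. What adjustment cannot do.** Suppose distress arising between surveys drives participation (wave-to-wave correlation 0.6 in two equal half-steps). A model adjusted for the preceding score then returns -1.16 (k = 0.5) and -0.43 (k = 1.0) against a true -2.0. Unadjusted, the figures are +0.01 and +1.53.

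**The case against.** A reader might infer that the planned analysis cannot estimate the programme effect at all, and can give only an undefined quantity or an indirect effect. The documents do not support that. The natural effect model is offered only as an example. If programming is meant as the exposure, which the stated goal of effectiveness makes plausible, the total effect (direct plus indirect) is the effectiveness quantity. Some regression-based mediation models also contain a programme-to-outcome coefficient. What stands is narrower: the plan does not say that either is the target, names no mediator for the first reading, and names no adjustment for either. Nor does it help to read mediation loosely as influence, because a mediation method does not then fit the question.

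A reader might also cite the sentence "This is an observational registry that does not include a planned intervention or exposure" as proof that no exposure exists. It stands under Adverse Events and explains why adverse event reporting does not apply. It says nothing about analysis variables and is not evidence here.

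It is fair to add that the registry is open-ended, that participation and many covariates are already collected, and that nothing is lost if the text is clarified before analysis. This bears on the cost of the change, not on the need for it. It is also fair that the illustrations say nothing about the effects this registry will find.

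**Conclusion.** The point holds in this form: Aim 2 promises an answer on effectiveness, and the plan as written does not secure one. On the most natural reading the estimate is an indirect effect of an unnamed exposure, which is not the programme effect. On other readings a programme effect could be obtained, but it is not named as the target and is not protected against need-driven participation, which can hide or reverse it.

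This conclusion rests on the text alone. The size is illustrative: for an assumed true effect of -2.0 points, the indirect effect spans +1.6 to -1.6 over the scenarios shown, and the coefficient without the preceding score spans -1.2 to +0.7. The text should be settled before Aim 2 is analysed, so that the choice among readings is not made with the results in view.

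**What to change.** Rewrite the Aim 2 paragraph of the Statistical Analysis Plan.

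- **Primary analysis:** the association of recorded programme participation, as a time-varying exposure in each between-survey interval, with Aim 1 scores at the next survey.
- **Contrast:** define the participation measure and its reference in advance, for example any versus none with adjustment for interval length, or participation per month. Enter concurrent programme types jointly in one model.
- **Adjustment:** all preceding survey scores, prior participation, cancer type, stage, treatment, age, age at diagnosis, gender and race. Handle repeated intervals by a mixed model, cluster-robust errors or a marginal structural model.
- **Existing members:** flag them or analyse them separately, since their programme use may pre-date their registry baseline.
- **Reporting:** an adjusted association under a stated assumption of no unmeasured confounding, not demonstrated effectiveness.
- **Mediation:** secondary only, with participation as the exposure and a named mediator such as social support.
- **Needs outcome:** the aims and the SAP describe needs over time, while the Data Collection Schedule table ticks the needs assessment at baseline only. Reconcile these before including or excluding it. The PHQ-9 timing conflict between that table and Registry Data Points is a separate point.

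The cost is SAP rewording, some extra analysis, a more cautious conclusion, and confirmation that participation dates and types are logged. Intervals with a missed survey at either end will need the missing-data rule that the SAP leaves open. The precision of the result is unknown, because the number of subjects is undetermined.
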